# CLINICAL TRIAL PROTOCOL SYNOPSIS

Company name	Boehringer Ingelheim
Original protocol date	06 Mar 2023
Revision date	19 Oct 2023
BI trial number	1402-0019
Title of trial	An open-label, fixed-sequence cross-over, two-period, phase I trial to evaluate the effect of multiple doses of BI 1358894 on pharmacokinetics of a combination of ethinylestradiol and drospirenone in healthy female subjects
Investigator	
Trial site	
Clinical phase	I
Trial rationale	o further inform on prescription possibilities of BI 1358894 together with oral contraceptives, this investigation of potential drug-drug interaction aims to assure safe and effective use of oral contraceptives if combined with BI 1358894
Trial objective	To investigate the effect of multiple oral doses of BI 1358894 on pharmacokinetics of ethinylestradiol (EE) and drospirenone (DRSP) (Yasmin®)
Trial endpoints	Primary endpoints:  • AUC \tau,ss , and C \text{max,ss} of EE and DRSP in plasma  Secondary endpoint:  • C \text{min,ss} of EE and DRSP in plasma
Trial design	Open-label, two-period, fixed-sequence with a run-in period
Number of subjects total entered on each treatment Diagnosis	32 32 Not applicable
Main inclusion criteria	Healthy female subjects, premenopausal, age of 18 to 35 years (inclusive), body mass index (BMI) of 18.5 to 29.9 kg/m² (inclusive)

c41232811-04 Trial Protocol

Page 3 of 84

Test product 1	BI 1358894, film-coated tablets, dose strength and
dose	
mode of administration	Oral with 240 mL of water after a continental breakfast
Test product 2	Yasmin®, film-coated tablets
dose	30 microgram ethinylestradiol + 3 milligram drospirenone q.d.
mode of admin.	Oral with 240 mL of water after a continental breakfast
Duration of treatment	
 
Run-in period: 
 
1 tablet of Yasmin® q.d. for 21-49 days
 
 
 
Reference treatment (Period 1): 
 
1 tablet of Yasmin® q.d on study days 1 – 21
 
 
 
Test treatment (Period 2): 
 
1 tablet of Yasmin® q.d. +1
 
on study days 1 – 21
 
 
 

Statistical methods	The effect of multiple doses of BI 1358894 on COC Yasmin® (EE+ DRSP) will be estimated by the ratios of the geometric means (test/reference) for the primary endpoints AUC t,ss , C max,ss and secondary endpoint C min,ss (of EE and DRSP separately). Additionally, two-sided 90% confidence intervals (CIs) will be provided. This method corresponds to the two one-sided t-test procedure, each at a 5% significance level. Since the main focus is on estimation and not testing, a formal hypothesis test and associated acceptance range will not be specified. The statistical model will be an analysis of variance (ANOVA) on the logarithmic scale including effects for "subjects" and "treatment". CIs will be calculated based on the residual error from the ANOVA.  Descriptive statistics will be calculated for all endpoints.

c41232811-04 Trial Protocol Page 4 of 84

Proprietary confidential information © 2023 Boehringer Ingelheim International GmbH or one or more of its affiliated companies

# FLOW CHART

Period	Visit	Day	Planned time (relative to first drug administration) [h:min]	Approximate clock time of actual day [h:min]	Event and comment	Safety laboratory	PK plasma, BI 1358894	PK plasma, COC	Exploratory PD serum 	12-lead ECG	Vital signs (BP, PR)	Suicidality Assessment 	Questioning for AEs and concomitant therapy 
SCR	1	-91 to -			Screening (SCR) 	$A^6$				X	X	X	
Run	2	-56 to -			Self-administration of COC	x 							Х
-in 		-7 to -1			Follow up call (COC free interval)								х
	3	1	0:00	08:00	Dosing COC 	$\mathbf{B}^{8}$		x 	x 				X
		2	24:00	08:00	Dosing COC 								X
		3	48:00	08:00	Dosing COC 								X
		4	72:00	08:00	Dosing COC 								X
		5	96:00	08:00	Dosing COC 								X
		6	120:00	08:00	Dosing COC 								X
		7	144:00	08:00	Dosing COC 								X
		8	168:00	08:00	Dosing COC 								X
		9	192:00	08:00	Dosing COC 								X
		10	216:00	08:00	Dosing COC 	x 							X
		11	240:00	08:00	Dosing COC 								X
		12	264:00	08:00	Dosing COC 								Х
		13	288:00	08:00	Dosing COC 								X
		14	312:00	08:00	Dosing COC 								X
-		15	336:00	08:00	Dosing COC 								X
Period 1		16	360:00	08:00	Dosing COC 								X
Per		17	384:00	08:00	Dosing COC 								X
		18	408:00	08:00									X
		19	432:00	08:00	Dosing COC 								X
		20	456:00	08:00	Dosing COC 								X
			466:00	18:00	Admission to trial site	x 					X		X
		21	479:30	07:30	Start of continental breakfast								X
			480:00	08:00	Dosing COC 			x 	x 				X
			480:30	08:30				X					X
			481:00	09:00				X					X
			481:30	09:30				X					X
			482:00	10:00	240 mL fluid intake			X					X
			482:30	10:30				X					X
			483:00	11:00		-		X					X
			483:30	11:30	040 7 0 11 1 7 12			X					X
			484:00	12:00	240 mL fluid intake, Lunch 			X					X

c41232811-04 Trial Protocol

Page 5 of 84

Period	Visit	Day	Planned time (relative to first drug administration) [h:min]	Approximate clock time of actual day [h:min]	Event and comment	Safety laboratory	PK plasma, BI 1358894	PK plasma, COC	Exploratory PD serum 	12-lead ECG	Vital signs (BP, PR)	Suicidality Assessment 	Questioning for AEs and concomitant therapy 
				13:00				X					X
			486:00	14:00				X					X
			488:00	16:00	Snack (voluntary) 			X					X
			490:00	18:00				X					X
			492:00	20:00	Dinner 			X					X
		22	504:00	08:00	Breakfast  , discharge from trial			X		X	X		X
					site								
		23-28			Follow-up call (COC free								X
					interval)								
	4	1	0:00	08:00	Dosing COC + BI 1358894 12	$\mathbf{B}^8$	x 	x 				$\mathbf{x}^2$	X
		2	24:00	08:00	Dosing COC + BI 1358894 12								X
		3	48:00	08:00	Dosing COC + BI 1358894 12								X
		4	72:00	08:00	Dosing COC + BI 1358894 12								X
		5	96:00	08:00	Dosing COC + BI 1358894 12								X
		6	120:00	08:00	Dosing COC + BI 1358894 12								
		7	144:00	08:00	Dosing COC + BI 1358894 12							x 	X
		8										А	X
			168:00	08:00	Dosing COC + BI 1358894 12								X
		9	192:00	08:00	Dosing COC + BI 1358894 12	Q.							X
		10	216:00	08:00	Dosing COC + BI 1358894 12	x8							X
		11	240:00	08:00	Dosing COC + BI 1358894 12								X
		12	264:00	08:00	Dosing COC + BI 1358894 12								X
		13	288:00	08:00	Dosing COC + BI 1358894 12								X
		14	312:00	08:00	Dosing COC + BI 1358894 12							$\mathbf{x}^2$	X
7		15	336:00	08:00	Dosing COC + BI 1358894 12								X
ро		16	360:00	08:00	Dosing COC + BI 1358894 12								X
Period 2		17	384:00	08:00									X
Ъ		18	408:00	08:00	Dosing COC + BI 1358894 12		x 						X
		19	432:00	08:00	Dosing COC + BI 1358894 12		x 						X
		20	456:00	08:00	Dosing COC + BI 1358894 12		x 						X
			466:00	18:00	Admission to trial site	$\mathbf{x}^{8}$					X	$\mathbf{x}^2$	X
		21	479:30	07:30	Start of continental breakfast								X
			480:00	08:00	Dosing COC + BI 1358894 12		x 	x 	x 				X
			480:30	08:30				Х					X
			481:00	09:00				Х					X
			481:30	09:30		1		X					X
			482:00	10:00	240 mL fluid intake			X					X
			482:30	10:30	J IIII IIIIII			X					X
			483:00	11:00		+		X					X
			483:30	11:30									
			484:00	12:00	240 mL fluid intake, Lunch 	+		X					X
			484:00	13:00	240 ml maid make, Lunch			X					X
			[contact]		1		X					X

c41232811-04 Trial Protocol Page 6 of 84

Period	Visit	Day	Planned time (relative to first drug administration) [h:min]	Approximate clock time of actual day [h:min]	Event and comment	Safety laboratory	PK plasma, BI 1358894	PK plasma, COC	Exploratory PD serum 	12-lead ECG	Vital signs (BP, PR)	Suicidality Assesssment 	Questioning for AEs and concomitant therapy 
			486:00	14:00				X					X
			488:00	16:00	Snack (voluntary) 			X					X
			490:00	18:00				X					X
			492:00	20:00	Dinner 			X					X
		22	504:00	08:00	Breakfast  , discharge from trial			X		X	X	X	X
					site								
		23-28			Follow-up call (COC free							X	X
					interval)								
EoS	5	42 to 52			End of study (EoS) examination 	C 				X	X	X	X

- Subject must be informed and written informed consent obtained prior to starting any screening procedures. Screening
  procedures include physical examination, check of vital signs, ECG, safety laboratory (including drug screening and
  cotinine test), demographics (including determination of body height and weight, smoking status and alcohol history),
  relevant medical history, concomitant therapy and review of inclusion/exclusion criteria. In addition, a gynaecological
  examination will be performed prior to trial entry.
- 2. Pre-dose
- 3. If several actions are indicated at the same time, the intake of meals will be the last action.
- 4. At the end of study (synonym for end of trial), the EoS examination includes physical examination, body weight, vital signs, ECG, safety laboratory, recording of AEs and concomitant therapies.
- 5. AEs and concomitant therapies will be recorded throughout the trial, but will be specifically asked for at the times indicated in the Flow Chart above.
- 6. Including hematology, biochemistry, coagulation, urinalysis, drug screen (only at screening), cotinine test (only at screening) and serum pregnancy test.
- 7. The intake of Yasmin® starts depending on the subjects' actual menstruation cycle and at least -28 days before Day 1 of first treatment period. In the run-in period, the subjects will take one tablet of COC daily until Day -8. On Day 7 to Day -1 no COC tablets will be given in order to induce withdrawal bleeding. Self-administration in the morning with no requirement of fasting. Self-administration to be documented in the diary. A negative urine pregnancy test should be performed at the site 1 to 7 days before start of the run-in. Details are outlined in Section 4.1.4
- 8. Urine pregnancy test. Additional urine drug screening on day 20 of each period.
- 9. Blood collection takes place within 10 minutes before dosing.
- 10. Suicidality assessment using the Columbia-Suicidal Severity Rating Scale (C-SSRS): 'Screening/Baseline' version at Visit 1, and 'since last visit' version at other visits.
- 11. Measurement of exploratory pharmacodynamic parameters: estradiol, luteinizing hormone (LH), follicle stimulating hormone (FSH), and progesterone. The samples will be taken in duplicate.
- 12. Dosing at the trial site after a continental breakfast (for details see Section 4.1.4).

c41232811-04 Trial Protocol

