## 1.2.2.3 Safety

Combined oral contraceptives (COC) including Yasmin® should not be used in the following conditions. Should any of the conditions appear for the first time during COC use, the product should be stopped immediately.

- Presence or risk of venous thromboembolism (VTE)
- Presence or risk of arterial thromboembolism (ATE)
- Presence or history of severe hepatic disease or liver tumors
- Current or history of breast cancer
- Hypersensitivity to the active substances or to any of the excipients

The frequency of diagnosis of breast cancer is very slightly increased among COC users. As breast cancer is rare in women under 40 years of age the excess number is small in relation to the overall risk of breast cancer. Causation with COC use is unknown.

The most common adverse events with Yasmin® are nausea, headache, migraine, depressed mood, menstrual cycle alteration, breast tenderness, vaginal discharge and candidiasis vulvovaginal altered mood, breast pain, and breast tenderness.

Less common adverse events are changes in the libido, hypertension, hypotension, vomiting, diarrhoea, acne, eczema, pruritus, alopecia, breast hypertrophy, vaginal infections, fluid retention and weight changes.

Rare adverse events are hypersensitive reactions, asthma, hearing loss, venous and arterial thromboembolism, erythema nodosum, erythema multiforme and discharge of the mammary glands.

Drospirenone, as many other progestogens, has been linked to increased risk of venous thromboembolism [R23-0501] A statement from FDA concluded that the increase in the risk of thromboembolism resulting from the use of drospirenone remains unclear; in its statement, the FDA mentioned that increased risk of venous thromboembolism with oral contraceptives such as drospirenone exists but remains lower than the risk of this condition during pregnancy and during the postpartum period [R23-0680].

c41232811-04 Trial Protocol

Page 19 of 84

Proprietary confidential information © 2023 Boehringer Ingelheim International GmbH or one or more of its affiliated companies

For a complete listing of adverse reactions including frequency of occurrence please refer to the current version of the summary of product characteristics (SmPC) [R23-0484].

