2.2.2.3 Safety and tolerability

Safety and tolerability of BI 1358894 will be assessed based on:

- Adverse events (including clinically relevant findings from the physical examination)
- Safety laboratory tests
- 12-lead ECG
- Vital signs (blood pressure, pulse rate)
- Suicidality assessment (C-SSRS)

Proprietary confidential information © 2023 Boehringer Ingelheim International GmbH or one or more of its affiliated companies

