## 3. DESCRIPTION OF DESIGN AND TRIAL POPULATION

#### 3.1 OVERALL TRIAL DESIGN

The trial will be performed as a non-randomised, open-label, two-period, fixed sequence trial with run-in period in healthy female subjects in order to compare the test treatment (T) to the reference treatment (R).

Reference (R): one tablet of Yasmin® q.d. after a continental breakfast on Days 1-21 in Period 1.

Test (T): one tablet of Yasmin® q.d.  $\pm$  one tablet of BI 1358894 25 mg q.d.  $\pm$  two tablets of BI 1358894 50 mg q.d. after a continental breakfast on Days 1-21 in Period 2.

[figure not shown]
The Reference Treatment will always be followed by the Test Treatment in a fixed sequence. There will be no wash-out period between the treatments.

All subjects will undergo a run-in period that starts between Day -56 and Day -28. In this period, the subjects will take one tablet of Yasmin® daily until Day -8.

In the last 7 days of each treatment period (i.e., Day 22 to Day 28) and the run-in period (i.e. Day -7 to Day -1) no treatment will be given in order to induce bleeding.

For details, refer to Section 4.1.

An overview of all relevant trial activities is provided in the Flow Chart. For visit schedule and details of trial procedures at selected visits, refer to Section 6.1 and 6.2, respectively.

Abbreviation: R=Reference Treatment (Yasmin®); T=Test Treatment (Yasmin® and BI 1358894)

Figure 3.1: 1 Trial design

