#### 3.3.4.1 Withdrawal from trial treatment

An individual subject will be withdrawn from trial treatment if:

- 1. The subject wants to withdraw from trial treatment. The subject will be asked to explain the reasons but has the right to refuse to answer
- 2. The subject has repeatedly shown to be non-compliant with important trial procedures and, in the opinion of both, the investigator and sponsor representative, the safety of the subject cannot be guaranteed as she is not willing or able to adhere to the trial requirements in the future. For details regarding missed visits see Section 6.1.
- 3. The subject needs to take concomitant medication that interferes with the investigational medicinal product or other trial treatment
- 4. The subject can no longer receive trial treatment for medical reasons (such as pregnancy, surgery, adverse events (AEs), or diseases)
- 5. The subject has an elevation of AST and/or ALT ≥3-fold ULN and an elevation of total bilirubin ≥2-fold ULN (measured in the same blood sample) and/or needs to be followed up according to the DILI checklist provided in the ISF
- 6. Suicidal ideation (type 2-5) or any suicidal behaviour based on C-SSRS questionnaires during the trial
- 7. The subject experiences a drug-related adverse event of severe intensity or a serious adverse event
- 8. In addition to these criteria, the investigator may discontinue subjects at any time based on his or her clinical judgment.
- 9. If it is known that a subject becomes pregnant during the trial, administration of the trial medication is to be stopped immediately, and the subject is to be removed from the trial. The subject is to be followed until she has given birth or until the end of the pregnancy. The subject's data are to be collected until the end of the trial (last visit of last subject) and reported in the CTR. For reporting of pregnancy and associated events, refer to Section 5.2.6.2.3.
- 10. If new efficacy or safety information becomes available, Boehringer Ingelheim will review the benefit-risk-assessment and, if needed, pause or discontinue the

c41232811-04 Trial Protocol

Page 34 of 84

Proprietary confidential information © 2023 Boehringer Ingelheim International GmbH or one or more of its affiliated companies

trial treatment for all subjects or take any other appropriate action to guarantee the safety of the trial subjects.

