#### 5.2.5 Other safety parameters

#### 5.2.5.1 Suicidality assessment

The C-SSRS is a semi-structured, investigator-rated interview, developed by clinical experts in cooperation with the FDA, assessing both suicidal behaviour and suicidal ideation. It does not give a global score, but provides some categorical and some severity information specifically for behaviour and ideation [R08-1147].

The C-SSRS interview may be administered by a physician or a study nurse with C-SSRS training. It has a typical duration of five minutes, and causes only a low burden on subjects. At a minimum, the interview consists of 2 screening questions related to suicidal ideation and 4 related to suicidal behaviour, and may be expanded to up to 17 items in case of positive responses. Free text entries are allowed.

The C-SSRS has been widely used in large multinational CTs. The C-SSRS will be administered at the screening visit (using the 'screening / baseline' version) with the aim to exclude subjects with active moderate or severe symptomatology within a specified time prior to the screening or baseline visit. The life time history of suicidal ideation and behaviour will also be recorded. See Section 10.1 for the original English C-SSRS. For this trial, the paper version of the respective German translation will be used. After the screening visit, the 'since last visit' version is used for the suicidality assessment at the time points indicated in the Flow Chart.

**Positive** reports are generated for any of the following findings:

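### No C-SSRS is scheduled from the first run-in dose until Period 2 Day 1, so withdrawal item 6 has no scheduled trigger during run-in or reference dosing (minor; cheap to improve)

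*Protocol*

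**What the plan says.** Protocol Section 5.2.5.1 fixes the timing. After screening, "the 'since last visit' version is used for the suicidality assessment at the time points indicated in the Flow Chart". Footnote 10 of the Flow Chart assigns the two forms: "Screening/Baseline' version at Visit 1, and 'since last visit' version at other visits". Read alone, the footnote could mean every later visit, but Section 5.2.5.1 limits it to the marked time points.

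The suicidality column of the Flow Chart reads:

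- Screening: marked.
- Run-in, including the call in the tablet-free week: blank.
- Period 1, Days 1 to 22 and the Day 23-28 call: blank.
- Period 2: marked at Day 1 (pre-dose), Days 7, 14, 20 and 22, and the Day 23-28 call.
- End of study: marked.

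Protocol Section 3.3.4.1, item 6, withdraws a subject from trial treatment for: "Suicidal ideation (type 2-5) or any suicidal behaviour based on C-SSRS questionnaires during the trial". It is not restricted to BI 1358894. Item 8 adds that "the investigator may discontinue subjects at any time based on his or her clinical judgment".

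Under Section 5.2.6.2.4, C-SSRS reports of ideation type 4 or 5, or of suicidal behaviour, have to be filed as SAEs. For ideation types 1 to 3, AE reporting is left to the investigator. Section 7.2.5 tabulates AEs by treatment and assigns them by recorded onset, while C-SSRS results themselves are only listed.

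**The concern.** Item 6 makes a C-SSRS finding a reason to stop treatment, and Yasmin is part of that treatment (it is test product 2 in Section 4.1.1). Section 1.2.2.3 names among its most common adverse events "nausea, headache, migraine, depressed mood". Yet the instrument that item 6 depends on is not scheduled while Yasmin is given alone. A subject who develops ideation in the run-in meets no scheduled C-SSRS before any of the 21 Period 1 doses.

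The second issue is unequal search. C-SSRS can generate SAEs, and these enter tables by treatment. During dosing the instrument is used only on test, so such SAEs are more likely to be recorded under test than under reference. Section 3.3.4.3 calls for immediate discontinuation of the trial after a single drug-related SAE. A positive interview in Period 2 would then have to be judged for causality without any C-SSRS taken during dosing with Yasmin alone.

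**Working it through.** **Inputs**

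- Run-in start, Section 3.1: "All subjects will undergo a run-in period that starts between Day -56 and Day -28".
- Last run-in tablet on Day -8 (Section 3.1). There is no Day 0, because Section 4.1.4 makes the day after the run-in Day 1 of Period 1.
- 21 Yasmin doses in each period, 28 days per period, no wash-out (Sections 4.1.4 and 6.2.2). Period 2 Day 1 is therefore Day 29 counted from Period 1 Day 1.
- Drospirenone residual effect period (REP) of 9 days. Protocol Section 1.2.3 gives both 6 and 9; its derivation (5 x 40 h = 8.3 days, rounded up) and SAP Section 6.1 both give 9, so 9 is used.

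**The plan's own figure.** Run-in doses = (-8) - (start day) + 1.

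- Start Day -28: -8 + 28 + 1 = 21.
- Start Day -56: -8 + 56 + 1 = 49.

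This matches the 21 to 49 days in the synopsis.

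**Length of the gap, first run-in dose to Period 2 Day 1**

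| Run-in start | Calendar days | Yasmin doses | Tablet-free days | Scheduled C-SSRS |
|---|---|---|---|---|
| Day -28 | 28 + 28 = 56 | 21 + 21 = 42 | 56 - 42 = 14 | 0 |
| Day -56 | 56 + 28 = 84 | 49 + 21 = 70 | 84 - 70 = 14 | 0 |

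**Interviews during dosing** (after a period's first dose and before its last). Reference: 0. Test: Days 7, 14 and 20 = 3. Period 2 Day 1 is before the first test dose and Day 22 is after the last, so neither counts. A stray character in the Period 2 Day 8 row looks like a reading error. If it were a mark, the test count would be 4 and the point would be the same.

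**Reach of the Period 2 Day 1 interview.** Last Period 1 dose on Day 21 to Day 29 = 8 days = 192 h, which is less than 9 x 24 = 216 h. It falls inside the reference REP and can place earlier events by recorded onset. By then all 42 to 70 doses have been taken.

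**Comparison with the other safety measures.** Laboratory panel B is on Day 1 of both periods, vital signs are on Days 20 and 22 of both, and ECG is on Day 22 of both. Only the suicidality column differs between periods.

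**With C-SSRS at Period 1 Day 1 pre-dose and Days 7, 14 and 20**

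- Period 1 doses still to come at each interview: 21 at Day 1, 15 at Day 7 (Days 7-21), 8 at Day 14 (Days 14-21) and 1 at the Day 20 evening admission (Day 21).
- Interviews during dosing: 3 against 3.
- Longest run of doses without a scheduled C-SSRS: from 42-70 down to 21-49, all in the run-in.

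**The case against.** The best defence is purpose. Section 2.2.2.3 introduces the list that contains C-SSRS with "Safety and tolerability of BI 1358894 will be assessed based on", and the schedule gives a screen, an interview before the first BI 1358894 dose, interviews on the drug and one at the end. The BI 1358894 risk rows of Table 1.4.2: 1 are not visible in this copy and may hold the rationale. This makes the schedule understandable. It does not fully explain the gap, because vital signs, ECG and laboratory tests stand in the same list and are matched across periods.

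It can also be said that item 6 tells the investigator what to do with a C-SSRS result and does not promise continuous testing. That is fair. A reader might infer that subjects are unprotected until Period 2, and the documents do not support this. AE questioning is scheduled in the run-in and on every Period 1 dosing day. It opens with general questions but allows specific ones. Withdrawal items 4, 7 and 8 apply throughout, early leavers should have the end-of-study visit with C-SSRS, and Section 3.3.3 excludes relevant psychiatric disorders, recent ideation or attempts, and past major depression. What these routes do not replace is the item 6 threshold: ideation of type 2 or 3 requires withdrawal but need not be reported as an AE.

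A third objection is that 0 against 3 depends on the window, since the Period 2 Day 1 interview belongs to the reference REP. That stands in part. The interview is a real look-back, so a reader should not infer that events in the gap would go unrecorded. It still cannot change dosing that is already over.

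A reader might also take the last visit in footnote 10 to be the Day 22 discharge, which would leave no Period 1 dose in the look-back. That reading is implausible: with daily attendance it would cut the Period 2 Day 7 and Day 14 look-backs to one day.

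**Conclusion.** The point holds as a minor, inexpensive improvement. For 56 to 84 days and 42 to 70 Yasmin doses, item 6 has no scheduled trigger, and C-SSRS during dosing is 0 on reference against 3 on test. The Period 2 Day 1 interview covers this stretch only in retrospect.

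A reader might infer that a treatment comparison is biased. The documents do not support that: the primary endpoints are pharmacokinetic, safety is descriptive without hypothesis tests, and C-SSRS is only listed. The exposed item is the recording of C-SSRS-generated SAEs in the by-treatment AE tables, and such events should be rare in this screened population.

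Nor did the Period 1 imbalance occur. SAP Section 4 says that no subject started Period 1. Only the run-in part of the gap applied, to the 28 subjects treated there (SAP Section 6.1), whose C-SSRS was at screening and end of study (SAP Section 7.9). The recommendation therefore matters for a restart or reuse of the design.

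The conclusion rests on reading the Flow Chart columns as extracted and on the 9-day drospirenone REP.

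**What to change.** Mark C-SSRS in the Period 1 rows of the Flow Chart at Day 1 pre-dose and at Days 7, 14 and 20, as in Period 2. The Day 1 interview lets a run-in event stop Period 1 dosing, and the other three equalise the search. Item 6 can stay as written. Stating in footnote 10 that the look-back runs from the last C-SSRS is optional wording.

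Cost: a Flow Chart amendment and four interviews per subject. The protocol says of one interview: "It has a typical duration of five minutes, and causes only a low burden on subjects". That is 4 x 5 = 20 minutes per subject and 20 x 32 = 640 minutes for 32 subjects, somewhat more if answers are positive. Subjects already attend the site for dosing on these days, so no new visit or instrument is needed. The change adds no interview within the run-in: its 21 to 49 self-administered doses would still be covered only by look-back from Period 1 Day 1.
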